#### **5. ANALYSIS POPULATIONS**

##### **5.1 Intent-to-Treat (ITT) Population**

All randomized subjects will be included in the ITT Population.

##### **5.2 Safety Population**

All subjects administered any amount of investigational product will be included in the Safety Population.

### **5.3 Per-Protocol (PP) Population**

The PP Population will include all randomized subjects who receive all doses of investigational product as required by the protocol and have no major protocol violations. Major protocol violations will be reviewed and the subjects in the PP population will be identified prior to unblinding the study.

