#### **Clinical investigation Duration (Per subject)**

Total Clinical investigation duration: (Recruitment period) + screening + treatment and evaluation + follow-up.

- Screening Period: 7 days to -4 hours
- Treatment: 7 Days
- Follow-up: 24 hours (± 2 hours) after first treatment; 8 days + 1 day) after first treatment
- End of clinical study: 15 days  $\pm$  1 day after first treatment

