#### Visit 4 (Day 9 + 1) Follow-Up to 7 Twice Daily Treatments:

The study subject will return for a follow-up evaluation to the clinical site on Day  $9 \pm 1$ day. At this follow-up visit, the subject will undergo the following procedures and evaluations.

- Vital signs measurements including weight, temperature, resting blood pressure, heart rate, and respiratory rate
- Baseline laboratory tests (blood chemistries and hematology)
- Visual examination of the ulcer
- Scoring of the Ulcer(s) using the DUSS and DFI Wound Scoring System
- Photo Documentation and Calculation of the Ulcer Area and Depth using the Aranz Medical SilhouetteTM
   System
- Collection of a sample from the ulcer for microbiological assessment

Subjects will be given a 7 day supply of non-abrasive bandage and written instructions on the proper care and hygiene to include keeping the ulcer clean and bandage dry until the Day 15 follow up visit. In addition, subjects will be told to call if there is any worsening of the ulcer with regard to pain, infection, or swelling.

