### 8.6 Study Visits

Subjects will have 5 nominally scheduled study visits: Screening (Day -7 to -4 hours), Single Dose Visit (Day 1), Safety Review and Multiple Dose Visit (Day 2), Safety Review Visit (Day  $9 \pm 1$  day) and Final Visit (Day  $15 \pm 2$  days). Additional visits for screening procedures and/or follow-up (e.g., in follow-up of Adverse Events) may be necessary.

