### 12.5 Visit 4 (Day 9 + 1) Follow-Up to 7 Twice Daily Treatments

The study patient will return for a follow-up evaluation to the clinical site on Day 9 + 1. At this follow-up visit, the patient will undergo the following procedures and evaluations.

- Vital signs measurements including weight, temperature, resting blood pressure, heart rate, and respiratory rate
- Baseline laboratory tests (blood chemistries and hematology)
- Visual examination of the ulcer
- Scoring of the Ulcer(s) using the DUSS and DFI Wound n System
- Photo Documentation and Calculation of the Ulcer Area and Depth using the Aranz Medical SilhouetteTM System
- Collection of a sample from the ulcer for microbiological assessment
- Collection of Subject Home Treatment Log
- Collection of Investigational Product (IP)

Patients will be given a 7 day supply of non-abrasive bandage and written instructions on the proper care and hygiene to include keeping the ulcer clean and bandage dry until the Day 15 follow up visit. In addition, patients will be told to call if there is any worsening of the ulcer with regard to pain, infection, or swelling.

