## 3. STUDY OVERVIEW

This is a phase 1/2a prospective, multi-center, blinded, randomized, dose escalation study. This study will be conducted at four investigational sites. Subjects with diabetic chronic foot ulcer(s) and a Diabetic Ulcer Severity Score (DUSS) of 0 to 3, ulcerated area(s) of not more than two ulcers between 0.5 and 6 cm^2, and no underlying DUSS Probing to Bone='Yes' are eligible to be enrolled into the study.

Doses of Nu-3 will be escalated in three planned sequential cohorts with 10 subjects in each cohort. Randomization will be 4:1 active to placebo in each cohort. The dose levels in each cohort are:

- Cohort 1 – 0.1% solution of Nu-3 in 0.9% saline with vehicle
- Cohort 2 – 1% solution of Nu-3 in 0.9% saline with vehicle
- Cohort 3 – 2% solution of Nu-3 in 0.9% saline with vehicle

Each cohort has placebo defined as 0.9% saline with vehicle. Dosing will be twice daily for 7 consecutive days.

Subjects will have scheduled study visits as follows:

- Screening (Day -7 to -4 hours)
- Single dose visit (Day 1)

- Safety review and multiple dose visit (Day 2)
- Safety review visit (Day 9  $\pm$ 1 day)
- Final Visit (Day 15  $\pm$ 2 days)

At the conclusion of each cohort, a Safety Review Committee will review the safety data and determined if it is safe to proceed to the next cohort. The committee includes, but is not limited to the Sponsor's designated Medical Monitor, the Medical Director of the CRO, and the Medical Director of Lakewood Amedex. Additional members can be added as the sponsor deemed appropriate.

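### Visit 4 has two windows (Day 9 ±1 and Day 9 +1); a Day 8 visit can end multiple dosing short of 14 applications, so a subject inside a stated window misses the all-doses per-protocol rule

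*SAP*

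**What the plan says.** **Day 9 ±1.** Protocol 8.6 lists "Safety Review and Multiple Dose Visit (Day 2), Safety Review Visit (Day" and completes the entry as 9 ±1. The synopsis text for Visit 4 says "The study subject will return for a follow-up evaluation to the clinical site on Day" and then gives 9 ±1. SAP 3 has "Safety review visit (Day 9" followed by ±1 day. The contents list prints the title of Protocol 12.5 with ±1. Protocol 8.10.2, which sets the data needed for dose escalation, calls the visit the Day 8 safety review visit.

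**Day 9 +1.** The schedule of events gives +1. Protocol 12.5 says "The study patient will return for a follow-up evaluation to the clinical site on Day 9 + 1". The synopsis heading, directly above the ±1 text, is "Visit 4 (Day 9 + 1) Follow-Up to 7 Twice Daily Treatments". The synopsis duration line has "8 days + 1 day) after first treatment"; with Day 1 as first treatment, 8 days later is Day 9.

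**Dosing.** Protocol 10.2 and 12.4 start the MAD regimen on Day 2, with the first application observed in clinic, and run it twice daily for 7 days. The home treatment log has two entries on each of 7 days. Protocol 12.5 has the product collected at Visit 4.

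**Per-protocol rule.** SAP 5.3 takes subjects who "receive all doses of investigational product as required by the protocol and have no major protocol violations". Protocol 16.2 has the same all-doses condition and lists under-dosing as a major violation. The synopsis asks only for 80% of expected doses. SAP 8.1 evaluates efficacy at the end of the MAD portion without naming the visit.

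**The concern.** The ±1 window lets a site see a subject on Day 8, which is still a dosing day even if two applications were made on Day 2. Collecting the kit at that visit ends treatment. Three things follow for such a subject:

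- The 7-day regimen is cut short.
- The end-of-MAD swab and scores are taken before dosing is complete.
- PP status depends on which text is read. The subject fails an all-doses rule counted as 14 applications, may pass the synopsis 80% rule, and has kept to a window that both documents state.

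The phrase in SAP 5.3 that ties the doses to what the protocol requires does not say whether doses given up at an in-window visit were still required. PP tables are planned for culture, DUSS, DFI score and components, and ulcer measurements, and each dose group has only 8 active subjects.

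**Working it through.** Neither document states a total number of applications, so there is no plan figure to reproduce. The count is made directly.

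**Inputs.** Two applications a day for 7 days (Protocol 10.2, 12.4; home log): 2 × 7 = 14. First MAD application on Day 2. Kit collected at Visit 4 (Protocol 12.5).

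**Formula.** Let V be the day of Visit 4, a the number of applications on Day 2 (1 or 2; the documents leave this open), and m the number made on the visit day before the kit is handed in. Applications received = min(14, a + 2 × (V − 3) + m).

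| Visit day | a | m = 0 | m = 1 |
|---|---|---|---|
| 8 | 2 | 2 + 10 = 12 (85.7%) | 13 (92.9%) |
| 8 | 1 | 1 + 10 = 11 (78.6%) | 12 (85.7%) |
| 9 | 2 | 2 + 12 = 14 | 14 |
| 9 | 1 | 1 + 12 = 13 (92.9%) | 14 |
| 10 | 1 or 2 | 14 | 14 |

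A late Day 8 visit after both of that day's applications (m = 2) gives 14 when a = 2, and 1 + 10 + 2 = 13 when a = 1.

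**Against the PP rules.** Anything under 14 misses the all-doses rule of SAP 5.3 and Protocol 16.2. The synopsis threshold is 0.80 × 14 = 11.2, so 12 or 13 meets it and 11 does not. If the Day 1 single dose is counted as well, 11 + 1 = 12 of 15 is exactly 80.0%.

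**What the correct window does alone.** Day 9 +1 removes the Day 8 cases. One case remains: a Day 9 visit after a single Day 2 application and no dose that morning still gives 13 of 14. The SAP therefore needs a sentence as well as a corrected window.

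**Size in the PP set.** One removal is 1 of 8 (12.5%) of a dose group. As an illustration with invented outcomes, take two-sided Fisher tests under the SAP's three cohorts (3 × 2 = 6 pooled placebo):

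- 5/8 v 0/6: (56 + 6)/2002 = 0.031.
- Remove an active success, 4/7 v 0/6: (35 + 15)/715 = 0.070.
- Remove an active failure, 5/7 v 0/6: (21 + 6)/1287 = 0.021.
- Remove a placebo failure, 5/8 v 0/5: (56 + 40 + 1)/1287 = 0.075.

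With the Protocol's five cohorts (5 × 2 = 10 pooled placebo), 5/8 v 0/10 is 56/8568 = 0.0065 and 4/7 v 0/10 is 35/2380 = 0.0147, both below 0.0167.

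**The case against.** **The conflict may come from PDF reading.** Some plus signs could be damaged plus-minus signs: the contents list has ±1 for Protocol 12.5, and the duration line has an unmatched bracket. This does not dispose of the point. The schedule prints +1 for Visit 4 next to an intact ±1 for Visit 5. If every location did read ±1, the inconsistency would go but the Day 8 shortfall would be allowed everywhere.

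**The synopsis 80% rule already admits these subjects.** At 12 or 13 of 14 it does, and this part stands: the failure arises only under SAP 5.3 and Protocol 16.2. Those are the detailed definitions, however, and the SAP does not carry the 80% rule.

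**An in-window subject has taken everything required.** That reading is open. Earlier protocol versions bound in the same file told subjects to treat until the evening before the next visit. The current text does not repeat this, and Protocol 16.2 counts under-dosing as a major violation.

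**Day 9 +1 may not be the intention.** Protocol 8.10.2 names Day 8, although that could be a count of days since first treatment. The title "Follow-Up to 7 Twice Daily Treatments" and the schedule favour a visit after dosing is complete.

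**PP membership is settled blind.** SAP 5.3 has PP subjects identified before unblinding. This guards against choosing by outcome, but gives the blind review no rule to apply.

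**The p-values are hand-picked.** They are. A reader might infer that the window puts significance at risk or favours one arm. The documents do not support that: they give no outcomes and no number of Day 8 visits, a removal can move the PP result either way, and the same example with ten placebo subjects crosses neither 0.05 nor 0.0167.

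**Conclusion.** The point holds and is minor. The documents give two windows for Visit 4, and the wider one allows a Day 8 visit that can end MAD dosing at 12 or 13 of 14 applications and bring the end-of-MAD assessment forward into the dosing period. The 12 or 13 assumes two applications on Day 2 and a visit before that day's dosing is finished; with one application on Day 2 it is 11 or 12. Such a subject misses the all-doses PP rule while keeping to a stated window. At 12 or 13 of 14 the synopsis rule would be met; at 11 of 14 MAD applications it would not.

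The number affected is unknown, and no subject would have a Day 8 visit if sites work from the schedule. ITT membership is unchanged, since it includes all randomized subjects. A reader might infer that the PP analysis is biased or that efficacy conclusions are in doubt; nothing in the documents establishes either.

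**What to change.** - Set Visit 4 to Day 9 +1 in the synopsis Visit 4 text, the contents list, Protocol 8.6 and SAP 3.
- In Protocol 8.10.2, change Day 8 to Day 9 for the safety review visit.
- In SAP 8.1, name Visit 4 as the end-of-MAD time point.
- In SAP 5.3, state that applications forgone because the kit was collected at an in-window Visit 4 are not missed doses. This also covers the Day 9 visit with 13 of 14.
- Make the synopsis PP rule agree with SAP 5.3.

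If Day 8 visits have already taken place, flag those assessments as on treatment and add a sensitivity analysis; otherwise neither is needed.

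The cost is five small text corrections, two SAP sentences and one aligned definition. No new data are needed and the ITT analysis set does not change. The downside is a visit window one day narrower: Days 9 and 10 instead of Days 8 to 10.

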## **6. SUBJECT DISPOSITION**

Subject disposition information will be summarized for all subjects by dose group. Summaries will include: the number of screened and screen failure subjects, the number of subjects in the ITT, Safety and PP Populations, the number of subjects completing the study, and the primary reason for discontinuing the study.

## **7. DEMOGRAPHIC AND BASELINE CHARACTERISTICS**

Demographic information (age, sex, race, and ethnicity) and baseline characteristics (height, weight and BMI) will be summarized by dose group. These demographic and baseline characteristics summaries will be analyzed for the Safety Population. Inferential testing is not planned on any demographic and baseline characteristic data.

## **8. EFFICACY ANALYSIS**

### **8.1 Definition of Efficacy Endpoints**

All efficacy endpoints will be summarized by visit and evaluated statistically at the end of the MAD portion of the study. Efficacy endpoints include:

- The proportion of subjects with a normal culture
- The change from baseline in the DUSS score
- The change from baseline in the DFI score
- The absence of each of the following as reported by the investigator on the CRF:
  - Purulent discharge
  - Nonpurulent drainage
  - Erythema
  - Induration
  - Tenderness
  - PainLocal warmth (no change)
- Data captured on the total wound size for each subject using the Aranz Medical Silhouette™ System:
  - Wound area (cm^2)

- Percentage of area reduction
- Perimeter (mm)
- Maximum depth (mm)
- Mean depth (mm)
- Volume (cm^3)
- Length (mm)
- Width (mm)

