#### 8.3 Cohorts

The dose of Nu-3 administered will be escalated in five planned sequential cohorts, with 10 subjects in each cohort, to be administered Placebo (0.9% saline) or Nu-3 doses of 0.1% solution of BisphosphocinTM Nu-3 in 0.9% saline (w/v) (Cohort 1), 1% solution of BisphosphocinTM Nu-3 in 0.9% saline (w/v) (Cohort 2), 2% solution of BisphosphocinTM Nu-3 in 0.9% saline (w/v) (Cohort 4), 10% solution of BisphosphocinTM Nu-3 in 0.9% saline (w/v) (Cohort 5) at twice daily for 7 consecutive days.

Additional cohorts may be enrolled, if needed, as provided by protocol.

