#### **4. GENERAL ANALYSIS CONSIDERATIONS**

The statistical analyses will be reported using summary tables and data listings. For all efficacy parameters, a comparison will be made of each active treatment group versus placebo using the appropriate statistical test. Unless otherwise indicated, all statistical tests will be two-sided and differences will be considered statistically significant if the associated p-value is less than 0.05. Continuous variables will be summarized with means, standard deviations (SD), medians, minimums, and maximums. Categorical variables will be summarized by counts and by percentage of subjects in corresponding categories. All data will be summarized by dose group (cohort), with all placebo subjects combined into one placebo arm.

Individual subject data obtained from the electronic data capture system, study lab, and any derived data will be presented by cohort for each subject in data listings.

The analyses described in this plan are considered *a priori*, in that they have been defined prior to database lock for individual subjects. Any analyses performed subsequent to database lock will be considered post-hoc and exploratory. Post-hoc analyses will be identified in the CSR.

All analyses and tabulations will be performed using SAS® Version 9.4 or higher on a Windows platform. Tables and listings will be presented in PDF format. Upon completion, all SAS® programs will be validated by an independent programmer. In addition, all program output will undergo a senior level statistical review. The validation process will be used to confirm that statistically valid methods have been implemented and that all data manipulations and calculations are accurate. Checks will be made to ensure accuracy, consistency with this plan, consistency within tables, and consistency between tables and corresponding data listings. Upon completion of validation and quality review procedures, all documentation will be collected and filed by the project statistician or designee.

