## **8.2 Analysis of Efficacy Endpoints**

For each dose group, the proportion of subjects with a normal culture at the end of the MAD portion of the study will be compared to the proportion of subjects with a normal culture at the end of the MAD portion of the study for the combined placebo group using a Fisher's exact test. A subject with a normal culture at this time will be considered a success. Any subject with a missing value at the end of the MAD portion of the study will not be included in the analysis. A p-value less than 0.05 will be considered statistically significant and a p-value less than 0.0167, employing a Bonferroni correction for multiple comparisons, will be considered highly conclusive.

For continuous efficacy endpoints, data will be summarized descriptively at and a comparison using the Wilcoxon Rank Sum test between each of dose groups and the combined placebo group will be performed at each visit. For these endpoints, no imputation for missing values will be performed.

For categorical endpoints, a Fisher's exact test will be performed in a similar manner. Subjects missing a value for a secondary endpoint will be considered a failure (counted in the denominator) for that endpoint.

For all tests, a p-value less than 0.05 will be considered statistically significant and a p-value less than 0.0167, employing a Bonferroni correction for multiple comparisons, will be considered highly conclusive. Analysis for each secondary endpoint will be performed on the ITT population and the PP population.

Ulcer measurements and percentage of area reduction will be summarized descriptively by visit and statistical testing using a Wilcoxon Rank Sum test between each dose group and the combined placebo group. For all tests, a p-value less than 0.05 will be considered statistically significant. Analysis for each additional endpoint will be performed on the ITT population and the PP population.

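### SAP 8.1 and 8.2 disagree on when efficacy is tested, and the 0.0167 'highly conclusive' threshold adjusts only for three doses, not for endpoints, visits or populations

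*SAP*

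**What the plan says.** **Timing.** SAP 8.1 separates description from testing: every efficacy endpoint is summarised by visit and "evaluated statistically at the end of the MAD portion of the study". SAP 8.2 handles the endpoint groups differently:

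- Culture is compared by Fisher's exact test at the end of MAD.
- For continuous endpoints, the Wilcoxon comparison "between each of dose groups and the combined placebo group will be performed at each visit".
- Categorical endpoints (the DFI components) are tested by Fisher's exact test in a like manner, with no time point named.
- Ulcer measurements are summarised by visit and tested by Wilcoxon, with no test time given in that paragraph.

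**Thresholds.** SAP section 4 sets the default: "Unless otherwise indicated, all statistical tests will be two-sided", at 0.05. In 8.2, the culture paragraph and the secondary-endpoint paragraph each give two tiers. The latter reads "For all tests, a p-value less than 0.05 will be considered statistically significant and a p-value less than 0.0167", and the lower threshold, "employing a Bonferroni correction for multiple comparisons, will be considered highly conclusive". The ulcer paragraph gives one tier only: "For all tests, a p-value less than 0.05 will be considered statistically significant". Secondary and ulcer endpoints are analysed in both ITT and PP. SAP section 8 sets no hierarchy, and no adjustment across endpoints, visits or populations.

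**Doses.** The SAP has "three planned sequential cohorts with 10 subjects in each cohort". Protocol 8.3 has doses "escalated in five planned sequential cohorts, with 10 subjects in each cohort".

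**The concern.** Because 8.1 covers all efficacy endpoints, it and the each-visit sentence in 8.2 cannot both govern the continuous ones. Two statisticians working from this SAP could run different sets of tests, and the larger set is more than twice the smaller. The choice could then be made after the results are seen.

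The second issue is what the labels claim. A Bonferroni threshold described as highly conclusive suggests that multiplicity has been dealt with. It has been dealt with only across doses, inside one endpoint at one visit. A secondary objective is to support the choice of dose range for later studies, so a chance result with that label at one dose could carry undue weight.

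**Working it through.** **1. The SAP's own figure.** 0.05 / 3 = 0.01667, which rounds to 0.0167. The threshold is a Bonferroni correction for three dose-versus-placebo comparisons and nothing else.

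**2. Inputs.**
- Doses: 3 (SAP section 3).
- Group sizes: 4:1 within cohorts of 10 gives 8 per dose and 2 placebo. Pooled over three cohorts, placebo is 6.
- Endpoints (SAP 8.1): culture 1, DUSS 1, DFI total 1, DFI components 7, ulcer measures 8; total 18.
- Post-dose visits (protocol section 2, Schedule of Events): DUSS and ulcer imaging on Days 2, 9 and 15; DFI on Days 9 and 15.

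**3. Number of tests.** Tests per dose = culture + DUSS visits + DFI visits + 7 × component visits + 8 × ulcer visits. Multiply by 3 doses.

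| Reading | Per dose | Three doses | Fisher / Wilcoxon |
|---|---|---|---|
| A. 8.1 governs: end of MAD only | 1+1+1+7+8 = 18 | 54 | 24 / 30 |
| B. DUSS and DFI total at each visit, the rest once | 1+3+2+7+8 = 21 | 63 | 24 / 39 |
| C. As B, with ulcer measures at three visits | 1+3+2+7+24 = 37 | 111 | 24 / 87 |
| D. As C, with components at two visits | 1+3+2+14+24 = 44 | 132 | 45 / 87 |

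**4. Expected false positives at 0.05 under no drug effect.** At nominal size these are 54 × 0.05 = 2.7 and 111 × 0.05 = 5.55. Exact tests in groups this small run below nominal. By enumeration at 8 versus 6, Fisher's test has size at most 0.0198, and the exact Wilcoxon test without ties has size 0.0426. Expected number = Fisher tests × 0.0198 + Wilcoxon tests × 0.0426:

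- A: 24 × 0.0198 + 30 × 0.0426 = 0.48 + 1.28 = about 1.8
- B: 24 × 0.0198 + 39 × 0.0426 = 0.48 + 1.66 = about 2.1
- C: 24 × 0.0198 + 87 × 0.0426 = 0.48 + 3.71 = about 4.2
- D: 45 × 0.0198 + 87 × 0.0426 = 0.89 + 3.71 = about 4.6

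These sums do not need the tests to be independent. Correlation changes how false positives cluster, not their expected number.

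**5. Reach of the 0.0167 tier.** In reading C the ulcer tests number 8 × 3 × 3 = 72, so the tier clearly applies to 111 − 72 = 39 tests (24 Fisher, 15 Wilcoxon). At 0.0167 the enumerated sizes at 8 versus 6 are at most 0.0071 (Fisher) and 0.0127 (Wilcoxon without ties). Expected false 'highly conclusive' results are then up to 24 × 0.0071 + 15 × 0.0127 = 0.17 + 0.19 = about 0.36. If the tier also reaches the ulcer tests, the figure is 24 × 0.0071 + 87 × 0.0127 = 0.17 + 1.10 = about 1.3. A Bonferroni correction over three comparisons holds the expected number to 0.05 within one endpoint and visit.

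**The case against.** The strongest case against is that little hangs on these p-values. The primary objective is safety, the study is a pilot with no sample size calculation, and escalation rests on safety data and dose-limiting toxicities. That stands, and it limits how serious the point is. It does not settle which tests are to be run or make the label accurate.

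Several stronger readings are tempting, and the documents do not support them:

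- *That 111 to 185 tests will be labelled significant or highly conclusive.* The counts are tests eligible for a label. The figure of 111 is one reading among 54 to 132. The figure of 185 is 37 × 5 and needs the protocol's five cohorts; the SAP plans three.
- *That everything is tested at unadjusted 0.05.* This leaves out the 0.0167 tier, to which the highly conclusive wording belongs.
- *That the label covers all 18 endpoints.* The ulcer paragraph restates only 0.05. The preceding paragraph does say all tests, so the tier's reach to the eight ulcer measures is unclear rather than established.
- *That 5.55 is the expected number of false positives for 111 tests.* It ignores the conservatism of exact tests. Ties lower the figure further, notably for DUSS, which scores pulses, probing to bone, location and number of ulcers and can be expected to change little in two weeks.
- *That ITT and PP double the problem.* They largely repeat the same comparisons in the same subjects.

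A fair objection to one possible remedy also stands. Keeping the labels for culture alone would conflict with protocol 16.5, which prespecifies the same two tiers for DUSS. Protocol section 16 also calls for comparison with placebo on all parameters.

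**Conclusion.** The point holds in a limited form. SAP 8.1 and 8.2 conflict on when continuous endpoints are tested, and the test time for DFI components and ulcer measures is unclear. The SAP therefore permits 54 to 132 tests per population with three doses. Expected false positives at 0.05 are up to about 1.8 for 54 tests and 4.2 for 111. The 0.0167 threshold corrects only for the three doses within one endpoint and visit. It clearly applies to the culture, DUSS, DFI and DFI-component tests, and the highly conclusive label overstates the control it gives.

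The sizes rest on these assumptions: 8 per dose against 6 pooled placebo with no missing data, exact tests, no ties in the Wilcoxon comparisons, and no drug effect on any endpoint. The SAP does not say whether the Wilcoxon p-values are exact. The change should be made, but the safety objective and pilot status keep it from being critical.

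**What to change.** - Amend SAP 8.2 so that every efficacy test is done at the end-of-MAD visit only, with other visits descriptive. Name that visit, since the SAP's visit list does not identify it.
- State that 0.0167 adjusts only for the three dose comparisons within an endpoint. Drop the highly conclusive wording, or limit it to culture and DUSS, as protocol 16.5 prespecifies.
- Report the remaining endpoints, including the ulcer measures, as exploratory: estimates, 95% confidence intervals and nominal p-values.
- If five cohorts are analysed, reconcile the divisor. 0.05 / 5 = 0.01, whereas protocol 16.5 prints 0.016 for that division and the SAP uses 0.05 / 3.

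The cost is SAP wording, settled before database lock, and fewer tests to run. Keeping the label for culture and DUSS stays within protocol 16.5. The downside is that fewer results can be called significant.
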